10.7. Laboratory Tests

Laboratory tests will be summarized at Baseline and Week 4. All tests listed in the table below will be collected in a non-fasting state (no food restrictions). In addition, laboratory safety tests may be performed at various unscheduled timepoints, if deemed necessary by the Investigator. All laboratory tests will be summarized (baseline, observed, change from baseline and percent change from baseline) by presenting descriptive statistics (number of subjects, mean, standard deviation, median, Q1, Q3, minimum, and maximum). A shift table describing out-of-normal range shifts will be provided for clinical laboratory results.

Hematology	Serum Chemistry
Hemoglobin	Blood Urea Nitrogen
Hematocrit	Bilirubin (total and direct)
Total and differential leukocyte count	Alkaline phosphatase
Red blood cell count with indices and morphology	Aspartate aminotransferase
Platelet count	Alanine aminotransferase
	Albumin
	Sodium
	Potassium
	Chloride
	Glucose
	Creatinine
Urinalysis	Additional Tests
pH	Urine pregnancy test ** (for females of childbearing potential only)
Specific gravity	Serum pregnancy test (hCG)***
Protein*	
Glucose	
Ketones	
Bilirubin	
Blood*	

Nitrite*	
Urobilinogen	
Leukocyte esterase*	
*	If urinalysis is positive for protein, blood, nitrite and/or leukocyte esterase, a microscopic examination (for red blood cells, white blood cells, bacteria, casts, and epithelial cells) will be performed.
**	At baseline and Week 4 for FOCBP only
***	At screening only

10.8. Electrocardiogram

12-lead electrocardiograms (ECGs) will be performed at Screening and Week 4. ECGs will be performed on subjects after 5 minutes in the supine position. ECGs will be summarized with descriptive statistics at each study visit.

10.9. Children's Depression Inventory 2 (CDI-2)

The CDI-2 assessment will be summarized at Baseline, Week 2, and Week 4. The CDI-2 quantifies depressive symptomatology and is recommended for use in initial evaluation and is appropriate when there is a need for an assessment and robust description of a child's depressive symptoms. This study will use the CDI Parent Report Form. The total score is the sum of the responses for the 17 questions. Total score, functional score, and emotional score will be summarized descriptively at each study visit.

CDI-2 total score is a sum of the 17 questions (individual questions scored as much or most of the time=3, often=2, some of the time=1, Not at all=0; range for score 0 to 51).

- CDI-2 emotional problem scale is a sum of 9 questions (Q1, Q3-6, Q8, Q10-12)
- CDI-2 function problem scale is a sum of 8 questions (Q2, Q7, Q9, Q13-17)

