### **6.5.2 Exclusion Criteria**

1. Subjects with any serious medical or psychiatric condition or clinically significant laboratory, ECG, vital signs, or physical examination abnormality that would prevent study participation or place the subject at significant risk, as judged by the Investigator.
2. Planned initiation or changes to concomitant medication that could, in the opinion of the Investigator, affect psoriasis vulgaris (e.g. beta blockers, ACE inhibitors).
3. Current diagnosis of non-plaque form of psoriasis (e.g., guttate, erythrodermic/exfoliative, palmoplantar only involvement, or pustular psoriasis). Current diagnosis of drug-induced psoriasis.
4. Subjects with any condition on the treatment area which, in the opinion of the Investigator, could confound efficacy measurements.
5. Subjects who cannot discontinue the use of strong cytochrome P-450 CYP3A4 inducers (e.g., efavirenz, nevirapine, glucocorticoids, barbiturates (including phenobarbital), phenytoin, rifampin, and carbamazepine) for 2 weeks prior to Baseline/Day 1 and during the study period.
6. Subjects who cannot discontinue the use of strong cytochrome P-450 CYP3A4 inhibitors (e.g., indinavir, nelfinavir, ritonavir, clarithromycin, itraconazole, ketoconazole, nefazodone, saquinavir, suboxone and telithromycin) for 2 weeks prior to Baseline/Day 1 and during the study period.
7. Subjects who are unwilling to refrain from prolonged sun exposure and from using a tanning bed or other artificial light emitting devices (LEDs) for 4 weeks prior to Baseline/Day 1 and during the study.
8. Subjects who cannot discontinue specific systemic therapies and/or topical therapies prior to the Baseline/Day 1 and during the study period according to [Table 1](#).
9. Current or a history of cancer within 5 years with the exception of fully treated skin basal cell carcinoma, cutaneous squamous cell carcinoma or carcinoma in situ of the cervix.
10. Subjects with any infection requiring oral or intravenous administration of antibiotics, antifungal or antiviral agents within 2 weeks prior to Baseline/Day 1.
11. Known or suspected:

- a. severe renal insufficiency or moderate to severe hepatic disorders (Child-Pugh B or C)
- b. history of chronic infectious disease (e.g., hepatitis B, hepatitis C, or human immunodeficiency virus (HIV))
- c. hypersensitivity to component(s) of the investigational products

12. Subjects with a CDI-2 (parent report) raw score >20 at Screening/Baseline

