## **6.6 Removal of Subjects from the Study**

Subject participation in this trial may be discontinued for any of the following reasons:

1. Occurrence of any medical condition or circumstance that, in the opinion of the Investigator, exposes the subject to substantial risk and/or does not allow the subject to adhere to the requirements of the Protocol.
2. Occurrence of a treatment-emergent adverse event (TEAE) or considerable worsening of an AE that, in the opinion of the investigator in consultation with the Medical Monitor and Sponsor, represents an unacceptable risk to the subject if he/she continues in the study. The investigator must follow the subject until the AE resolves or satisfactorily stabilizes.
3. Pregnancy
4. Subject's decision to withdraw from the study.
5. Weight loss of >5% if not dieting and after consultation with the Sponsor, at the Investigator's discretion.
6. CDI-2 raw total score of 34, after consultation with a mental health professional, the Sponsor, and at the Investigator's discretion.
7. Requirement for use of prohibited concomitant medication after consultation with the Sponsor and Medical Monitor.
8. Subject's repeated failure to comply with protocol requirements or study related procedures.
9. The subject interrupts trial study drug application for more than 50% of scheduled doses.
10. Termination of the study by the Sponsor, FDA, or other regulatory authorities.

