### Instructions:

For each of the statements below, select one response that best describes your observations of your child in the **PAST TWO WEEKS**.

Indicate your response for each item by **circling** the number that best corresponds to your choice. You may change an item response by drawing an **X** through your original choice and selecting a new response.

Remember, for each statement, pick **one** answer that best describes your observations of your child in the **PAST TWO WEEKS**.

My child...	Not at all	Some of the time	Often	Much or most of the time
1. looks sad.	0	1	2	3
2. has fun.	0	1	2	3
3. does not like himself or herself.	0	1	2	3
4. blames himself or herself for things.	0	1	2	3
5. cries or looks tearful.	0	1	2	3
6. is cranky or irritable.	0	1	2	3
7. enjoys being with people.	0	1	2	3
8. thinks that he or she is ugly.	0	1	2	3
9. has to push himself or herself to do schoolwork.	0	1	2	3
10. has trouble sleeping at night.	0	1	2	3
11. looks tired or fatigued.	0	1	2	3
12. seems lonely.	0	1	2	3
13. enjoys school.	0	1	2	3
14. spends time with friends.	0	1	2	3
15. is showing worse school performance than before.	0	1	2	3
16. does what he or she is told.	0	1	2	3
17. has disagreements and conflicts with others.	0	1	2	3

Copyright © 2011 [name] and Multi-Health Systems Inc. All rights reserved.  
In the United States, [name], [name]. In Canada, [name].  
[name], [name], [contact]. Internationally, [contact]. Fax, [contact] or [contact].

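### SAP 10.9 adds all 17 CDI-2 items in one direction although five describe healthy behaviour, so the function scale runs backwards and the total cannot be read against the 20 and 34 cut-offs

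*SAP*

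**What the plan says.** SAP 10.9 sets one rule for turning responses into numbers: "individual questions scored as much or most of the time=3, often=2, some of the time=1, Not at all=0". It makes no exception for any item. It then states that "The total score is the sum of the responses for the 17 questions", with "range for score 0 to 51". The subscales are plain sums as well: "CDI-2 emotional problem scale is a sum of 9 questions (Q1, Q3-6, Q8, Q10-12") and "CDI-2 function problem scale is a sum of 8 questions (Q2, Q7, Q9, Q13-17"). Total, functional and emotional scores are all to be summarized at Baseline, Week 2 and Week 4.

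The form itself is in Protocol Appendix 2. It prints 0, 1, 2, 3 in the same order beside every item. Twelve items describe symptoms or problems. The other five describe a child who is doing well: having fun (2), "enjoys being with people" (7), liking school (13), seeing friends (14) and doing as told (16).

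The protocol uses the score as a measure of severity. Section 6.5.2 excludes "Subjects with a CDI-2 (parent report) raw score >20 at Screening/Baseline". Section 6.6 lists as a ground for removal "CDI-2 raw total score of 34, after consultation with a mental health professional", and section 7.9 attaches prompt referral and possible discontinuation of study drug to the same score of 34.

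Neither document mentions reverse scoring or refers the reader to a scoring manual.

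**The concern.** A scale of functional problems should rise as function worsens. Five of its eight items here do the opposite: a parent who reports that the child no longer has fun, likes school or sees friends lowers the score. A real loss of interest would be tabulated as improvement, and in the total it would cancel worsening on the emotional items.

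This matters because safety is a primary endpoint and psychiatric events are a known effect of the active substance. Protocol 4.3.5 reports them in 5.9% of patients on oral roflumilast against 3.3% on placebo, with some cases of suicidality. Protocol 4.4 counts the mood questionnaire among the measures meant to detect expected adverse events, and the CDI-2 is the only mood instrument in the schedule. There is no control arm, so change from baseline in this score is the main structured evidence on mood.

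If sites add the form in the way the SAP does, the exclusion and referral rules are also misapplied: some well children are excluded and some unwell children are not referred.

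**Working it through.** **Inputs.** Item wording and response values come from Protocol Appendix 2, scoring and subscale membership from SAP 10.9, and cut-offs from Protocol 6.5.2, 6.6 and 7.9.

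**The plan's own figures.** 9 emotional + 8 function = 17 items, with no gap or overlap. 17 × 3 = 51, which reproduces the stated maximum. Reversing items leaves the range at 0 to 51, so a range check cannot reveal the problem.

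**Notation.**
- N = sum of the 12 negatively worded items, 0 to 36.
- P = sum of the five positively worded items (2, 7, 13, 14, 16), 0 to 15.
- M = sum of the three negatively worded function items (9, 15, 17), 0 to 9.

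**Formulas.**
- SAP total = N + P; reversed total = N + (15 − P).
- SAP function = M + P; reversed function = M + (15 − P).
- All nine emotional items are negatively worded, so that scale is the same either way.
- SAP total minus reversed total = 2P − 15, which runs from −15 to +15.

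**Children of uniform severity s.** Negative items are answered s and positive items 3 − s, so N = 12s, M = 3s and P = 15 − 5s.

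| s | SAP function | Reversed function | SAP total | Reversed total |
|---|---|---|---|---|
| 0 | 0 + 15 = 15 | 0 | 0 + 15 = 15 | 0 |
| 1 | 3 + 10 = 13 | 8 | 12 + 10 = 22 | 17 |
| 2 | 6 + 5 = 11 | 16 | 24 + 5 = 29 | 34 |
| 3 | 9 + 0 = 9 | 24 | 36 + 0 = 36 | 51 |

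The SAP function score falls as the child worsens. The SAP total rises, but it starts at 15 and covers 21 points where the reversed total covers 51.

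**At the exclusion cut-off (more than 20).** A child with all five healthy behaviours at 3 and six symptoms at 1 has N = 6 and P = 15. The SAP total is 21 (excluded); the reversed total is 6. In general, a SAP total of 21 corresponds to a reversed total of 36 − 2P, anywhere from 6 to 36.

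**At the referral score (34).** The child with s = 2 scores 29 under the SAP and exactly 34 when reversed. A SAP total of 34 corresponds to a reversed total of 49 − 2P, anywhere from 19 to 49. A child with none of the healthy behaviours (P = 0) needs N = 34 of a possible 36 to reach 34 under the SAP, against N = 19 when reversed.

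**Change from baseline.** Suppose each positive item drops one category (P falls by 5) while the emotional items rise by 5 points in all. The SAP total changes by +5 − 5 = 0; the reversed total changes by +5 + 5 = +10.

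**The case against.** The documents do not say how sites obtain the raw score for the 20 and 34 rules or where those cut-offs come from. Protocol 7.1.6 calls the appendix an example of a form, and that form is a copyrighted third-party instrument whose scoring instructions are not reproduced. Sites apply the rules during the trial under the protocol, whereas the SAP governs later tabulation. Sites may therefore be scoring correctly. That stands: an effect on eligibility and referral is a risk and has not been shown.

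Some limits of degree also stand. Three of the eight function items run the right way, so the scale is mixed with a net reversal and is not a mirror image. The emotional scale is unaffected and is reported separately. The profiles above are constructed; they show what can happen, and the documents give no response distribution from which to say how often. The study has about 20 children and is descriptive. Mood is also covered by open-ended adverse event questioning and diary review (Protocol 7.7.4) and by a referral rule for suicidal ideation that does not use the score (7.9).

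None of this repairs SAP 10.9. The section ties the value 3 to a response label, so it specifies the scoring itself and leaves no step at which reversal could already have happened. Program validation would not catch the fault either, because SAP section 5 has outputs checked for consistency with the plan.

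**Conclusion.** The concern holds. The fault is in the rule as written: a programmer who follows it exactly produces a function score that goes from 15 to 9 as a child goes from healthiest to most impaired, where it should go from 0 to 24. The total can differ from the correctly directed one by up to 15 points either way.

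The conclusion rests on two readings. First, items 2, 7, 13, 14 and 16 describe healthy behaviour, which is plain from the form. Second, a higher score is meant to be worse, which is inferred from the scale names and from the use of high scores to exclude and refer. The second reading fits the numbers: a referral score of 34 sits two-thirds of the way up a reversed scale of 51, but only 2 points below the 36 that the most symptomatic child can reach under the SAP rule.

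Confidence is high for the SAP-derived total and function score. Any effect on enrolment or referral depends on site practice. The printed form carries no reversal instruction, so a site adding the circled numbers would make the same error. This should be corrected before any CDI-2 score is derived.

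**What to change.** - In SAP 10.9, state that items 2, 7, 13, 14 and 16 are scored as 3 minus the response before the total and function scale are summed. The emotional scale needs no change.
- Derive every CDI-2 score from item-level data and do not use totals entered by sites.
- Confirm in writing that the cut-offs in Protocol 6.5.2, 6.6 and 7.9 refer to the reversed total, and send sites a scoring clarification.
- List any child whose eligibility or referral status differs between the two scorings.

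The cost is two SAP sentences, one clarification to sites and a re-derivation. No new data are needed provided item responses are held in the database. The SAP implies this by building its scores from the 17 responses, but it should be checked. The comparison of eligibility and referral status is a small additional task for study operations.

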10.10. Dermal Imaging

Medical photography will be performed at participating sites on consenting/assenting subjects and summarized at Baseline, Week 2, and Week 4. Subjects who are unwilling to participate in the medical photography will be allowed to opt out of this procedure and document on the informed consent form. Medical photography information will be presented in a by-subject listing.

11. Pharmacokinetics

Plasma levels of circulating roflumilast and its major N-oxide metabolite will be measured at the following time points:

- All enrolled subjects will have a trough PK sample at the Week 4 visit.
- A subset of 6 subjects who consent will have an additional PK sample collected pre-dose at the Week 2 visit.

PK concentration will be summarized by nominal time point. In addition, PK parameters and concentration listing will be presented as well. A detailed description of the PK analysis will be presented in a separate pharmacokinetics report.

12. Planned Tables, Figures, and Listings

A table of contents for the tables, listings, and figures will be presented in a separate document as the list of summaries or numbering may change after finalization of this document. If additional summaries are added that are not described in this document, then this SAP will be amended, or an addendum will be created.
